1. LIST OF ABBREVIATIONS

Abbreviation	Definition
ACR	American College of Rheumatology
AE	Adverse Event
AEM	Adverse Event Monitoring
CDAI	Clinical Disease Activity Index
CRP	C-Reactive Protein
DAS28	Disease Activity Score-28
DCP	Data Collection Point
eCRF	electronic Case Report Form
EDP	Exposure During Pregnancy
EULAR	European League Against Rheumatism
GSUS	Grey-scale Ultrasonography
HAQ	Health Assessment Questionnaire
IEC	Independent Ethics Committee
IRB	Institutional Review Board
MKUS	Musculoskeletal Ultrasonography
NIS	Non-Interventional Study
PDUS	Power Doppler Ultrasonography
PtGA	Patient Global Assessment of disease
RA	Rheumatoid Arthritis
SAE	Serious Adverse Event
SAP	Statistical Analysis Plan
SDAI	Simplified Disease Activity Index
SJC	Swollen Joint Count
SmPC	Summary of Product Characteristics
TJC	Tender Joint count
TNF-alpha	Tumor Necrosis Factor Alpha
US	Ultrasound
US7	Seven-joint ultrasound

3. AMENDMENTS AND UPDATES

On January 26, 2015, the recruitment status was as follows: 34 patients included in the cohort 1st biological versus 4 in the cohort 2nd biological.

For our predictive model, we need 100 evaluable patients but the cohort in which the patients are recruited will not impact the results.

In order to have 100 evaluable patients for the predictive model and given the above mentioned recruitment status, we decided to amend the protocol to allow the needed number of patients to be recruited in whichever cohort: 1st or 2nd. This will limit the potential extension of the recruitment period. [REDACTED]

4. MILESTONES

Milestone	Planned date
Completion of feasibility assessment	30 June 2014
Start of data collection	15 July 2014
End of data collection	30 June 2016
Interim report 1	30 January 2017
Final study report	31 May 2017

5. RATIONALE AND BACKGROUND

[figure not shown]
Today, both in clinical studies and clinical practice the Disease Activity Score-28 (DAS28) is the golden standard for measuring disease activity in rheumatoid arthritis (RA).

In the 2013 guidelines from the European League Against Rheumatism (EULAR) for the management of RA, recommendation 2 clearly states: “Treatment should be aimed at reaching a target of remission or low disease activity in every patient.”

This same article mentions that remission as defined by the DAS28 <2.6 is not regarded as sufficiently stringent to define remission, referring to the 2011 EULAR/American College of Rheumatology (ACR) remission criteria (Figure 1):

- Clinical Practice: the Boolean definition (SJC<1, TJC<1 and PtGA<1) and CDAI \leq 2.8 (SJC= Swollen Joint Count, TJC= Tender Joint Count, PtGA= Patient Global Assessment of disease, CDAI= Clinical Disease Activity Index)
- Clinical Studies: the Boolean definition (SJC<1, TJC<1 and PtGA<1, CRP <1) and SDAI \leq 3.3 (CRP= C-Reactive Protein, SDAI= Simplified Disease Activity Index)

Figure 1. Percentage of subjects maintaining remission as a function of time and criteria (Prince et al., 2012)

Only one study has evaluated these new criteria in a real life clinical practice. The article by Prince et al. (year and reference at the end of the protocol) concludes that in an RA population, only a minority of patients is in sustained remission. Further evaluation of these criteria in observational studies is needed.

Musculoskeletal ultrasonography (MKUS) has emerged as a tool with the potential to enhance disease assessment and management in this area. This includes applications in patients with undifferentiated arthropathy attending an early inflammatory arthritis clinic, in which the diagnosis of inflammatory disease may be confirmed or refuted at an early stage, and those with treated RA where accurate measurement of outcomes, such as response to therapy, structural damage and disease remission, are extremely important. This imaging modality is safe and portable, making it ideal for outpatient and inpatient settings, and can be used to assess many joints in multiple planes and to demonstrate changes in disease activity and structural damage over time. US is gaining popularity among rheumatologists, as increasing evidence supports the added value of a physician-performed ultrasonography assessment above traditional clinical, laboratory and radiographic measures, enabling greater confidence in diagnostic and management decisions (Brown, 2009, Dougados et al., 2010; Iagnocco et al., 2008). Remission when defined by clinical remission criteria (DAS, simplified disease activity index, etc...) does not always equate to the complete absence of inflammation as measured by US (Wakefield et al., 2012).

The new seven-joint ultrasound (US7) score was proposed by Backhaus et al. (2009). This is the first MKUS composite scoring system, combining soft tissue lesions (synovitis and tenosynovitis/paratenonitis) and destructive processes (erosions) in a single scoring system. The US7 score includes MKUS examination of the following joints of the clinically more affected side: wrist, MCP II and III, PIP II and III, MTP II and V. The joints are examined by Grey-Scale Ultrasonography (GSUS) and Power Doppler Ultrasonography (PDUS) for synovitis and tenosynovitis/paratenonitis from a dorsal and palmar/plantar aspect, and for erosions from a dorsal, palmar/plantar and radial/lateral (only MCP II and MTP V) aspect. Synovitis in GSUS is analysed semiquantitatively (0–3) according to Scheel et al. (2005): 0: absence; 1: small hypoechoic/anechoic line beneath the joint capsule (mild synovitis); 2: elevation of the joint capsule parallel to the joint area (moderate synovitis); 3: strong distension of the joint capsule (severe synovitis) (see Figure 2 and Figure 3).

Figure 2. Semi-quantitative (grade 0-3) grey-scale ultrasound synovitis score at the wrist joint in the dorsomedian longitudinal axis

[figure not shown]

Figure 1 Semi-quantitative (grade 0-3) grey-scale ultrasound synovitis score at the wrist joint in the dorsomedian longitudinal axis.

Figure 3. Semiquantitative (grade 0-3) grey-scale ultrasound synovitis score at the metacarpophalangeal II/III joints in the palmar longitudinal axis

[figure not shown]

Figure 3 Semiquantitative (grade 0-3) grey-scale ultrasound synovitis score at the metacarpophalangeal II/III joints in the palmar longitudinal axis.

The PDUS evaluation for synovitis (see Figure 4 and Figure 5) and tenosynovitis/paratenonitis is scored according to the scoring system of Szkudlarek et al. (2003).

Tenosynovitis/paratenonitis and erosions in GSUS are registered on a binary basis (0/1).

Figure 4. Semiquantitative (grade 0-3) power Doppler ultrasonography synovitis score at the wrist joint in the dorsomedian longitudinal axis

[figure not shown]

Figure 2 Semiquantitative (grade 0-3) power Doppler ultrasonography synovitis score at the wrist joint in the dorsomedian longitudinal axis.

Figure 5. Semiquantitative (grade 0-3) power Doppler ultrasonography synovitis score at the metacarpophalangeal II/III joints in the dorsal longitudinal axis

[figure not shown]

Figure 4 Semiquantitative (grade 0-3) power Doppler ultrasonography synovitis score at the metacarpophalangeal II/III joints in the dorsal longitudinal axis.

A recently published US7 reliability study investigated the inter-observer and intra-observer reliability of sonographers, determining the US7 score under conditions similar to those of daily rheumatological practice. The median overall κ value for detecting synovitis was $\kappa=0.51$, for tenosynovitis/paratenonitis $\kappa=0.57$ and for erosions $\kappa=0.45$. This study also showed that the US7 score has the potential also in multicentre analysis to assess structural changes with moderate to good reliability (Ohrndorf et al. 2012).

In today's clinical practice, there is still an existing need to define which remission criterion can best be used to predict remission in the long run.

There is a tendency to link (sustained) remission with a dose down strategy. However, dose down often results in flaring of the disease and flare rates go as high as 70% in this dose down population, expressing an urgent need for better defining the pool of patients in which dose down could be an option to consider.

6. RESEARCH QUESTION AND OBJECTIVES

This study aims both to evaluate remission according to different criteria and to look at which remission criterion at Month 6 is the most predictive for remission at Month 12.

6.1. Primary Objective

To determine which remission criterion at Month 6 predicts remission at Month 12 the best.

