Time	0 m	Month 3 (2-4)	Month 6 (5-7)	Month 9 (8-10)	Month 12 (11-13)
Demographics	X				
Disease duration	X				
DAS28	X	X	X	X	X
SDAI	X	X	X	X	X
CDAI	X	X	X	X	X
BOOLEAN CDAI SJC≤1, TJC≤1, PtGA≤1	X	X	X	X	X
BOOLEAN SDAI SJC≤1, TJC≤1, PtGA≤1 and CRP≤1	X	X	X	X	X
Ultrasound (Selected Centers)	X		X		X
HAQ	X	X	X	X	X
Current medication	X	X	X	X	X
Adverse events	X	X	X	X	X

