7.5. Study size

It will not be possible to justify the sample size of the study on the basis of inferential statistical assumptions. Indeed, there are currently insufficient data available concerning the prediction of remission on the basis of CDAI, SDAI, DAS28, DAS28 and Ultrasound, and EULAR Boolean definition for clinical practice and clinical studies.

The analysis of the primary endpoint will be based on a logistic regression defining the dependent variable as the remission at Month 12 and the 5 independent variables as CDAI, SDAI, DAS28, DAS28 and Ultrasound, and EULAR Boolean definition for clinical practice and clinical studies.

This analysis will be conducted in each arm of the study if possible as well as after pooling of both patient groups.

In this context it seems reasonable to ensure the completion of the study by a total approximate number of 100 patients (approximately 50 patients per arm). In order to ensure 50 completers in each arm, 70 patients will be recruited at baseline, taking into account a drop out rate of 30% over 1 year period. In order to have 100 evaluable patients for the predictive model and given the current recruitment status (January 26th 2015 RA 1st: 34 vs RA 2nd: 4) we will allow the needed number of patients to be recruited in whichever cohort: 1st or 2nd. This will limit the potential extension of the recruitment period.

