7.7. Data analysis

Detailed methodology for summary and statistical analyses of data collected in this study will be documented in a SAP, which will be dated, filed and maintained by the sponsor. The SAP may modify the plans outlined in the protocol; any major modifications of primary endpoint definitions or their analyses would be reflected in a protocol amendment.

The analysis of the primary endpoint will be based on a logistic regression defining the dependent variable as the remission at month 12 and the 5 independent variables as CDAI, SDAI, DAS28, DAS28 and Ultrasound, and EULAR Boolean definition for clinical practice and clinical studies. This analysis will be conducted in each arm of the study as well as after a pooling of both patient groups.

The other statistical methods used for the analysis of the data will be mainly descriptive.

Appropriate inferential analyses will be used to compare the over-time modifications of study parameters and potentially to compare the two arms of the study.

Time to event variables will be analyzed using the Kaplan-Meier's method with comparison between groups being ensured by the log rank test.

An interim analysis of baseline data will be performed at Month 6.

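### The primary objective is to name the best Month 6 criterion, but the protocol gives no performance measure, no interval on differences between criteria and no allowance for selection

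*Combined protocol and SAP*

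**What the plan says.** The primary objective (6.1) is a selection: "To determine which remission criterion at Month 6 predicts remission at Month 12 the best". On method, 7.7 states: "The analysis of the primary endpoint will be based on a logistic regression defining the dependent variable as the remission at month 12". The predictors are given in 7.5 as "5 independent variables as CDAI, SDAI, DAS28, DAS28 and Ultrasound, and EULAR Boolean definition for clinical practice and clinical studies". The analysis is to be run pooled and in each arm; 7.5 adds that the by-arm analysis is done if possible.

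On size, section 3 says "For our predictive model, we need 100 evaluable patients", and 7.5 plans "a total approximate number of 100 patients (approximately 50 patients per arm"). Section 7.5 also concedes that this number has no inferential basis.

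The inferential comparisons named in 7.7 are changes over time, possibly the two arms, and a log-rank test for time-to-event variables. None is between criteria. For everything outside the primary analysis, 7.7 says: "The other statistical methods used for the analysis of the data will be mainly descriptive". Detailed methodology is deferred to a SAP, and the document contains no SAP text.

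Table 1 defines the two Boolean criteria as "BOOLEAN CDAI SJC≤1, TJC≤1, PtGA≤1" and "BOOLEAN SDAI SJC≤1, TJC≤1, PtGA≤1 and CRP≤1". The second is the first plus CRP. DAS28 with ultrasound likewise builds on DAS28.

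**The concern.** A claim that one criterion predicts best is a claim about differences between criteria measured on the same patients. The protocol gives a model but does not say what makes one criterion better than another, how precisely the differences will be known, or what is concluded when the leaders are close. With overlapping criteria and about 100 patients, chance alone will usually put one of them on top, and the performance of whichever comes first is flattered by having been chosen.

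Section 5 presents the choice of criterion as an unmet need in practice. A ranking whose first place cannot be told apart from second would be a weak answer to that need, and a reader of the report could not see how weak.

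**Working it through.** **The plan's own figure.** Section 7.5 recruits 70 per arm for 50 completers at 30% dropout. 50/(1−0.30) = 71.4, and 70 × 0.70 = 49 per arm, or 98 in two arms. About 100 evaluable patients is therefore consistent with the recruitment plan. The 100 itself cannot be derived, because no alpha, power or effect size is given.

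**Number of candidates.** The text says five. Counting the two Boolean definitions separately, as Table 1 does, gives six. In a setting run both ways (latent correlation 0.90, 30% remission, n=100), a single winner emerged in 94% of studies with five criteria and 93% with six.

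**Simple precision check.** If two criteria classify equally well and a share d of patients is classified correctly by only one of them, the 95% half-width of the paired difference in accuracy is 1.96 × √(d/n). The values of d are assumptions.

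| d | n=100 | n=50 |
|---|---|---|
| 5% | ±4.4 points | ±6.2 points |
| 10% | ±6.2 | ±8.8 |
| 20% | ±8.8 | ±12.4 |
| 30% | ±10.7 | ±15.2 |

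The n=50 column stands for one arm, or for a subset with ultrasound, which section 7.1 limits to selected centres.

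**Simulation of the ranking.** All inputs are assumptions: n=100, six binary criteria each met by 30% of patients, 35% in remission at Month 12, every criterion with the same true AUC of about 0.69, correlation between criteria 0.43 to 0.79, and 4,000 simulated studies per setting. Each criterion is scored on its own as AUC = (sensitivity + specificity)/2.

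- One criterion ranks alone at the top in about 91–97% of studies, although all are equal.
- The winner's AUC exceeds the truth by 0.042–0.050 at moderate overlap (0.43–0.59) and 0.028–0.036 at strong overlap (0.70–0.79).
- The SD of the difference between two criteria is 0.034–0.056, so the 95% range runs from 1.96 × 0.034 = ±0.07 to 1.96 × 0.056 = ±0.11.
- If one criterion is truly better by 0.02, it ranks first in about 29–35% of studies; if better by 0.05, in about 56–59%. Chance is 1/6 = 17%.

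**Sensitivity.** A second set of runs varied remission from 20% to 50% and latent correlation from 0.80 to 0.95. At n=100, a single winner emerged in 89–96% of studies, the median gap between best and worst was 0.05–0.10 by chance alone, and the paired 95% half-width was ±0.06 to ±0.12. At n=50, the half-width grew to ±0.09 to ±0.17 and the median gap to 0.08–0.14. Ties became more common, so a single winner emerged in 76–91%.

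**The case against.** The strongest reply is that the protocol is not the whole plan. Section 7.7 defers detail to a SAP that may modify what the protocol outlines, and the SAP could contain a paired comparison. This stands: the point is about what the protocol states. A reader might infer that the study will read off a winner, stop there and report a tie as a finding. The documents do not support that, because no section states any selection rule.

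Second, AUC appears nowhere in the plan, and the planned model enters several criteria together, so the simulation illustrates a single-criterion ranking rather than the stated analysis. This also stands. But the plan offers no other measure to simulate, and intervals on coefficients from a joint model are not intervals on differences in predictive performance.

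Third, the inputs are assumed. Giving every criterion 30% ignores differences in stringency: the studies Boolean cannot be met more often than the practice Boolean, and section 5 calls DAS28 remission insufficiently stringent. The strength of overlap is inferred from shared components and is not given. The results are therefore shown as ranges.

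Fourth, a reader might infer that the ranking is mostly noise or that a winner is certain. Neither follows. A true gap of 0.05 is found more than half the time, and exact ties occurred in about 4–11% of the wider runs at n=100.

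Finally, the sentence in 7.7 about mainly descriptive methods concerns the other analyses, not the primary one. Dose reduction appears in section 5 as background and in none of the objectives, so this study should not be described as selecting patients for it.

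**Conclusion.** The concern holds as a gap in the protocol. The primary objective asks for a best criterion, and the stated analysis has no measure, interval or allowance for selection with which to show that first differs from second. Under the stated assumptions, at n=100, a single winner emerges in about 91–97% of studies of equally good criteria. Its AUC is too high by about 0.03–0.05, and two criteria would need to differ by roughly 0.07–0.11 before a paired 95% interval excluded zero. Analyses by cohort or within an ultrasound subset would be less precise.

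The exact sizes depend on the remission rate, the overlap and the choice of AUC, none of which the documents give. That one criterion usually leads by chance held in every setting tried. It is not established that the SAP lacks a comparison, or that the study would necessarily report an unsupported winner.

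**What to change.** Amend 7.7 as follows:

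1. Name one definition of remission at Month 12 as the dependent variable. The protocol does not say which criterion defines it, and no performance measure can be computed until it does.
2. Name one performance measure, for example the AUC of each criterion on its own, and say whether the two Boolean definitions count as one candidate or two.
3. Report each criterion's optimism-corrected performance and paired bootstrap 95% intervals for the differences between criteria in the same patients (for example 2,000 resamples of patients). Repeat the choice of top criterion in each resample, so that the correction covers the selection.
4. Make comparisons that involve ultrasound only in patients who have ultrasound, and state their number.
5. Call a criterion best only where these intervals support it. Otherwise list the criteria that cannot be distinguished, with the share of resamples in which each ranks first. How strict to be, for instance whether to use simultaneous intervals against all others, is a choice to fix in advance.

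No new patients, visits or data are needed. The cost is wording and some programming, plus a less decisive message: at this sample size the conclusion will often be that the criteria cannot be distinguished.

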6.2. Secondary Objectives

- Describe the percentage of patients in remission at the different DCPs (Data Collection Points) according to different remission criteria: CDAI, SDAI, DAS28, DAS28 in combination with Ultrasound, EULAR Boolean definition for clinical practice and clinical studies.
- Describe percentage of the same patients in remission at the different DCPs, according to different remission criteria: CDAI, SDAI, DAS28, DAS28 in combination with Ultrasound, EULAR Boolean definition for clinical practice and clinical studies.
- Determine if the quantitative change in between baseline and Month 6 is predictive for the change at Month 12.
- Determine which single component is the most predictive for the composite index of remission.
- Determine predictors for remission, according to all the different criteria at each timepoint.
- Comparison between DAS28 remission and US remission

- Prediction of remission based on US data

7. RESEARCH METHODS

7.1. Study design

This will be an observational, multicenter study, in which patients with RA will be recruited in 2 cohorts. The study design can be found in Figure 6.

The first cohort is a cohort in which the decision by the treating rheumatologist has been taken to start treatment with Enbrel as first biological product, according to prevailing reimbursement criteria in Belgium and dosing in line with the Summary of Product Characteristics (SmPC).

The second cohort is a cohort in which the decision of the treating rheumatologist has been taken to start treatment with Enbrel according to prevailing reimbursement criteria in Belgium as second biological product (either after use of another anti-TNF or another mechanism of action) and dosing in line with SmPC.

The study flow chart can be found in Table 1.

At baseline, demographics, disease duration (defined as the time between diagnosis and etanercept treatment initiation), Health Assessment Questionnaire (HAQ) and different remission criteria (DAS28, SDAI, CDAI, Boolean definition of both CDAI and SDAI, DAS28 in combination with US) will be recorded.

The evaluation will take place at Data Collection Points (DCPs) which will coincide with regular visits, not scheduled for the purpose of the study, but at Q3 months with a time window of \pm one month, recording the same data, as well as current medication and related adverse events (AEs).

The ultrasound will only take place in selected centers with a proven record of US training and day-to-day clinical experience. Bruyn et al. (2013) concluded that the scoring of US intra-reader variability was excellent ($\kappa=0.91$) and inter-reader variability was good ($\kappa=0.75$).

A recently published US7 reliability study investigated the inter-observer and intra-observer reliability of sonographers, determining the US7 score under conditions similar to those of daily rheumatological practice. The median overall κ value for detecting synovitis was $\kappa=0.51$, for tenosynovitis/paratenonitis $\kappa=0.57$ and for erosions $\kappa=0.45$. This study also showed that the US7 score has the potential also in multicentre analysis to assess structural changes with moderate to good reliability (Ohrndorf et al. 2012).

Ultrasound images will be collected and saved. When needed for analysis, they can afterwards be read by central readers.

Figure 6. Study design

[figure not shown]

Table 1. Study flow chart

	Baseline	DCP1	DCP 2	DCP 3	DCP 4
Time	0 m	Month 3 (2-4)	Month 6 (5-7)	Month 9 (8-10)	Month 12 (11-13)
Demographics	X				
Disease duration	X				
DAS28	X	X	X	X	X
SDAI	X	X	X	X	X
CDAI	X	X	X	X	X
BOOLEAN CDAI SJC≤1, TJC≤1, PtGA≤1	X	X	X	X	X
BOOLEAN SDAI SJC≤1, TJC≤1, PtGA≤1 and CRP≤1	X	X	X	X	X
Ultrasound (Selected Centers)	X		X		X
HAQ	X	X	X	X	X
Current medication	X	X	X	X	X
Adverse events	X	X	X	X	X

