7.2. Setting

7.2.1. Inclusion criteria

Patients must meet all of the following inclusion criteria to be eligible for inclusion in the study:

1. Patients with active RA who start treatment with Enbrel according to the prevailing reimbursement criteria in Belgium and dosing in line with the SmPC.
 - a) First cohort: Enbrel is the first biological product prescribed.
 - b) Second cohort: Enbrel is the second biological product prescribed.
2. Capable of understanding and willing to provide signed and dated written, voluntary informed consent before any protocol-specific procedures are performed.
3. Eighteen (18) years of age or older at time of consent.
4. Evidence of a personally signed and dated informed consent document indicating that the patient (or a legally acceptable representative) has been informed of all pertinent aspects of the study.

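### The primary regression includes DAS28 with ultrasound, but ultrasound is done only in selected centres and the study size allows only for dropout, so a complete-case fit may use fewer than the 100 patients the model is said to need

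*Combined protocol and SAP*

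**What the plan says.** **Primary analysis.** Section 7.5 states: "The analysis of the primary endpoint will be based on a logistic regression", with remission at Month 12 as the dependent variable. Section 7.7 repeats this and lists "the 5 independent variables as CDAI, SDAI, DAS28, DAS28 and Ultrasound, and EULAR Boolean definition for clinical practice and clinical studies". The model is to be fitted in each arm (section 7.5 adds a proviso that this be possible) and after pooling.

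**Ultrasound.** Section 7.1: "The ultrasound will only take place in selected centers with a proven record of US training and day-to-day clinical experience". Tables 1 and 2 carry the same restriction, and Table 1 schedules the scan at baseline, Month 6 and Month 12. DAS28, SDAI, CDAI and the two Boolean definitions have no centre restriction and are planned at every visit.

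**Eligibility.** Section 7.2.1 admits "Patients with active RA who start treatment with Enbrel according to the prevailing reimbursement criteria in Belgium", subject to consent and age. It does not require that the centre performs ultrasound.

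**Study size.** Section 3: "For our predictive model, we need 100 evaluable patients". Section 7.5 aims for about 100 completers, about 50 per arm, and to reach 50 per arm says that "70 patients will be recruited at baseline, taking into account a drop out rate of 30% over 1 year period". The amended text, which opens "In order to have 100 evaluable patients for the predictive model", continues: "we will allow the needed number of patients to be recruited in whichever cohort: 1st or 2nd".

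The protocol does not define *evaluable*. It gives no number of ultrasound centres, no expected share of patients with ultrasound and no rule for patients without it. Detailed methods and variable definitions are deferred to a separate SAP that is not in the supplied text, and part of section 3 is redacted.

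**The concern.** A regression needs a value of every predictor for each patient it uses. One of the five predictors here depends on a scan that only some centres perform. A patient who completes the study elsewhere therefore has all the clinical criteria and the clinical components of the Month 12 assessment, but lacks one predictor. Under ordinary complete-case fitting that patient drops out of the whole model.

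Two things are at stake for the primary objective, which is to find the Month 6 criterion that best predicts Month 12 remission:

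- The model may fall short of the number that the sponsor set for it and amended the protocol to protect.
- The criteria that need no ultrasound would be ranked on fewer patients than the study collects, and only in centres selected for ultrasound experience. The ranking may not carry over to the other centres.

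**Working it through.** **Step 1. The plan's own figure (section 7.5).** Inputs: 50 completers per arm and 30% dropout.

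- Required recruitment: 50 / (1 − 0.30) = 71.4, so 72 per arm against 70 stated. This is close enough to confirm that dropout alone explains the figure.
- Forward check: 70 × 0.70 = 49 per arm; 2 × 70 = 140 recruited; 140 × 0.70 = 98 completers.

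The step from 100 to 140 is used up by dropout. Nothing is left for missing ultrasound.

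**Step 2. Worst case.** Let *s* be the share of completers with ultrasound. It is not in the documents, so a range is assumed. If every patient without a scan is dropped, the model keeps 98 × *s*.

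**Step 3. Smaller loss under one possible definition.** The documents do not define remission by DAS28 with ultrasound. Suppose it requires DAS28 remission as well as a clear scan. A patient not in DAS28 remission at Month 6 is then a non-remitter whatever the scan shows and can be classified without it. With *r* the share in DAS28 remission (assumed 30% to 50%, and equal in both kinds of centre), the usable share is (1 − *r*) + *r* × *s*. At *s* = 0.5:

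- *r* = 0.3: 0.70 + 0.15 = 0.85, and 98 × 0.85 = 83.3
- *r* = 0.5: 0.50 + 0.25 = 0.75, and 98 × 0.75 = 73.5

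| Assumed *s* | Kept, worst case (98 × *s*) | Lost, worst case | Kept, *r* = 0.3 | Kept, *r* = 0.5 |
|---|---|---|---|---|
| 1.0 | 98 | 0 | 98 | 98 |
| 0.9 | 88 | 10 | 95 | 93 |
| 0.7 | 69 | 29 | 89 | 83 |
| 0.5 | 49 | 49 | 83 | 74 |
| 0.3 | 29 | 69 | 77 | 64 |

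In the last two columns every lost patient is a DAS28 remitter from a centre without ultrasound, while non-remitters from those centres stay in. The loss is smaller but depends on one of the criteria being compared.

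**Step 4. If 100 patients with ultrasound were intended.** Recruitment across all centres would be 100 / (0.70 × *s*): 143 at *s* = 1.0, 159 at 0.9, 205 at 0.7, 286 at 0.5 and 477 at 0.3. The protocol gives no such figure.

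**The case against.** **The amended text may already cover this.** Being evaluable for the predictive model could mean having that model's inputs, with recruitment continuing until 100 patients qualify. In that case 98 is not the denominator, since it comes from the per-arm sentence whose split the amendment relaxed. This reading is open. However, section 7.5 also ties the 100 to completing the study, and neither section 3 nor section 7.5 mentions ultrasound as a condition. Even on this reading, patients without ultrasound would remain outside the ranking of the clinical criteria.

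**The missing SAP or the redacted text may hold a rule.** That is possible, and it limits confidence. Complete-case fitting is an assumption here; the protocol names no method for missing data.

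**The regression might be fitted one criterion at a time.** The text does not say that the five variables enter together, although one joint model is the more literal reading. Separate fits on whoever has each criterion would rank DAS28 with ultrasound on different patients from the rest, which mixes centre differences into the comparison.

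**Ultrasound has its own secondary objectives.** Section 6.2 does list them, but that does not take ultrasound out of the primary model.

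**Stronger readings to avoid.** A reader might infer that the trial loses half its patients. That is the worst case at one assumed share. A reader might infer a loss of power, but section 7.5 disclaims any inferential basis and sets no power or precision target. A reader might also turn the counts into standard-error ratios, for example 1/√0.5 = 1.41. That is at most an upper bound. It compares with a model that could not be fitted on all 98 if some lack ultrasound, it ignores step 3, and it is not the gain from the fix, which changes the model.

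**Conclusion.** The point holds in conditional form. The documents establish that the primary model includes an ultrasound predictor, that ultrasound is restricted to selected centres, that eligibility is not so restricted, and that the only stated allowance is dropout. If *evaluable* does not require ultrasound and not every recruiting centre performs it, a complete-case fit of the model as written falls below the sponsor's 100, leaves out clinical-criteria data planned at every visit, and ranks those criteria only in ultrasound-centre patients.

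The size of the loss cannot be computed from the documents. Across assumed shares of 30% to 90%, the worst case keeps 29 to 88 of 98; partial classification keeps more, with a selective loss. At a share of 100% there is no loss. The plan should be changed, because a better analysis is available from data already planned. Confidence is medium, given the missing SAP and the redaction.

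**What to change.** In sections 7.5 and 7.7:

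- Compare CDAI, SDAI, DAS28 and the Boolean definitions in all evaluable patients, against a Month 12 remission outcome that does not need ultrasound.
- Compare DAS28 with ultrasound against the other criteria only within ultrasound-centre patients, with every criterion assessed on the same patients.
- Define *evaluable*, state that the 100 refers to the clinical-criteria comparison, and give the expected size of the ultrasound subset separately.

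The cost is a protocol amendment with matching SAP text; section 7.7 itself says that major changes to the primary analysis would be reflected in an amendment. No new data collection is needed. The downside is a stated sample below 100 for the ultrasound criterion. The change adds no patients to that comparison, but it stops ultrasound availability from limiting the comparison of the other criteria.
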